#### 3. STUDY DESIGN

## 3.1. General Description

This study aims to evaluate the efficacy and safety of infusions of efgartigimod, a human neonatal crystallizable fragment receptor (FcRn) antagonist that can rapidly reduce IgG, including pathogenic antibodies. Efgartigimod has the potential to successfully treat pSS and improve disease manifestations by the reduction of IgG autoantibodies in pSS.

This is a randomized, double-blinded, placebo-controlled, phase 2, multicenter study, with an open-label extension (OLE) study.

For participants not enrolling in the OLE study, the study duration is approximately 36 weeks,

spanning the following study periods:

- Screening:  $\leq 4$  weeks
- Treatment: 24 weeks
- Follow-up: 56 days (after final dose)

For participants enrolling in the OLE study, the study duration is approximately 28 weeks, spanning the following study periods:

Document:

Author:

Version Number:

V2.0

Version Date:

31JAN2024

Template No.: CS TP BS016 Revision 7 Reference: CS WI BS005

Effective Date: 01Nov2021

Statistical Analysis Plan

Page 19 of 78

Screening: ≤ 4 weeksTreatment: 24 weeks

The study population includes adult participants with pSS, per ACR/EULAR 2016 classification criteria, with at least a moderate level of systemic disease activity (ESSDAI  $\geq$  5). Participants will be randomized using interactive response technology (IRT) to receive efgartigimod IV 10 mg/kg or placebo in a 2:1 ratio, respectively.

#### Treatment and Dosing:

Upon confirmation of eligibility at baseline, the participant will be randomized, stratified by IgG value at screening (> 16.0 g/L or  $\leq$  16 g/L).

All participants will receive efgartigimod IV 10 mg/kg or placebo once weekly for 24 weeks during the treatment period. Treatment will be administered as an approximately 1-hour IV infusion by site staff or a home nurse. The final dose will be administered at week 23.

At week 24, eligible participants may roll over to a single-arm OLE study.

Document:

Author:

Version Number:

V2.0

Version Date:

31JAN2024

Template No.: CS TP BS016 Revision 7

Reference: CS WI BS005

Effective Date: 01Nov2021

[figure not shown]
Statistical Analysis Plan

Page 20 of 78

 $This is a \ double-blinded \ study. \ The \ IRT \ will \ be \ programmed \ with \ blind-breaking \ instructions.$ 

Figure 1: Study Overview

Figure 1: ARGX-113-2106 Study Overview

ACR=American College of Rheumatology; D=day; ESSDAI=EULAR Sjögren's syndrome disease activity index; EULAR=European Alliance of Associations for Rheumatology; IV=intravenous; n=number of participants; OLE=open-label extension; pSS=Sjögren's syndrome; SS-A=anti-Sjögren's syndrome-related antigen A; SWSF=stimulated whole salivary flow (rate); UWSF=unstimulated whole salivary flow (rate); W=week

### 3.2. Sample Size

Participants are randomized in a 2:1 ratio (efgartigimod: placebo) to achieve approximately 15 randomized participants with an IgG value at screening > 16.0 g/L and 15 participants without an IgG value at screening > 16.0 g/L.

Effective Date: 01Nov2021

Statistical Analysis Plan

Page 21 of 78

Assuming 50% of the 20 randomized efgartigimod participants are CRESS responders, the 95% 1-sided confidence limit lower bound for the proportion of responders is approximately 33% (Wilson score interval). Placebo response rates ranging from 24% to 32% have been reported.

Therefore the target sample size should provide sufficient precision of the efgartigimod treatment effect at week 24 for planning future studies.

#### 3.3. Schedule of Activities

Schedule of activities can be found in Section 1.3 of the protocol.

## 3.4. Changes to Analysis from Protocol

- For this SAP, Estimand are defined for the study in Table B. The primary estimand for the study is to
  assess the proportion of CRESS responders on ≥ 3 of 5 items at week 24 in efgartigimed IV compared to
  placebo, considering the participant who discontinued study treatment or used prohibited concomitant
  medication.
- The histology of the parotid gland (Immunohistochemistry- The relative counts of lymphocytic infiltrate (stained for CD45), B/B+T cell ratio) will be considered as – Exploratory endpoint and not as secondary endpoint.

- 4. Data for the following biomarker endpoints will be received and processed by the sponsor:
  - a. Autoantibodies in serum including Anti-Ro/SS-A and Anti-La/SS-B
  - c.
  - d.

Document:

Author:

Version Number:

V2.0

Version Date:

31JAN2024

[figure not shown]
Template No.: CS TP BS016 Revision 7 Reference: CS WI BS005

Effective Date: 01Nov2021

Statistical Analysis Plan

Page 22 of 78

## 4. PLANNED ANALYSES

The following analyses will be performed for this study:

- 1. Interim Analysis at the end of treatment phase
- 2. Final Analysis

#### 4.1. Data Monitoring Committee

There will be no Data monitoring Committee for this study.

#### 4.2. Interim Analysis

One interim analysis (IA) will take place for this study once all the participants have either completed the week 24 assessments or discontinued the study prior to week 24. The results of the interim analysis will be based on unblinded treatment groups.

Derivations and definitions for the interim analysis will be based on those required for the final analysis contained in this SAP, unless deviations are stated within the text. The list of outputs provided with the full set of output templates (planned for the final analysis) will highlight which of these outputs will also be provided for the interim

 Document:
 Version Number:
 V2.0

 Author:
 Version Date:
 31JAN2024

 Template No.:
 CS TP BS016 Revision 7
 Reference:
 CS WI BS005

Effective Date: 01Nov2021

Statistical Analysis Plan

Page 23 of 78

analysis.

The interim analysis will be performed by IQVIA Biostatistics following authorization of this SAP, database lock, analysis sets and unblinding of treatment. The IQVIA study team, including those responsible for creating the programs to produce the outputs for the interim analysis, will remain unblinded. The Unblinding Plan will have all the details about Unblinded Team members.

## 4.3. Final Analysis

All final, planned analyses identified in this SAP will be performed by IQVIA Biostatistics following authorization of this SAP, database lock, analysis sets and unblinding of treatment.

Pharmacokinetic analysis is being performed by the IQVIA PK group in conjunction with the IQVIA Biostatistics group. PK concentration listings and summary statistics are described in this SAP. A separate PK analysis plan will be prepared to describe planned population PK/PD analysis.

#### 5. ANALYSIS SETS

Agreement and authorization of participants included/excluded from each analysis set for IA and Final Analysis, will be conducted prior to the unblinding of the study.

#### 5.1. Enrolled Analysis Set [ENR]

The enrolled analysis set (ENR) will contain all participants who provided informed consent.

### **5.2.Full Analysis Set [FAS]**

The full analysis set (FAS) will contain all randomized participants who received at least one dose of IMP and classified as Planned Treatment.

## 5.3. Safety Analysis Set [SAF]

The safety analysis set (SAF) will have - All participants exposed to IMP. Participants will be assigned in the

Document:

Author:

Version Number:

V2.0

Version Date:

31JAN2024

Template No.: CS TP BS016 Revision 7 Reference: CS WI BS005

Effective Date: 01Nov2021

Statistical Analysis Plan

Page 24 of 78

efficacy analyses according to the IMP they received. Data from these participants will be classified according to actual treatment received. The actual treatment arm will be the same as the planned treatment arm unless the participant received IMP other than the planned one for the whole study.

## **5.4.Efficacy Analysis Set [EAS]**

The efficacy set contains all subjects from the FAS that are, based on pre-randomization information, eligible for efficacy evaluation.

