# 9.2. Analysis Sets

The following analysis sets are defined:

Analysis set	Description
Full analysis set	All randomized participants who receive IMP. Participants will be assigned in the efficacy analyses according to the IMP they received.
Safety analysis set	All participants exposed to IMP. Participants will be assigned in the efficacy analyses according to the IMP they received.

The full analysis set will be used to analyze endpoints related to the efficacy objectives, and the safety analysis set will be used to analyze the endpoints and assessments related to safety.

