## 9.3.2. Primary Endpoint Analysis

The primary endpoint is response on  $\geq 3$  of 5 items of CRESS at week 24. The 5 items are systemic disease activity (clinESSDAI), patient-reported symptoms (ESSPRI), tear gland function (Schirmer's test, OSS), salivary gland function (UWSF, SGUS), and serology (serum IgG and RF).

A 95% Wilson Score CI for the proportion of CRESS responders will be presented for both treatment groups. This will be provided for all full analysis set participants and by IgG stratum at screening (> 16.0 g/L or  $\leq 16 \text{ g/L}$ ) for the efgartigimod treatment group.

Additionally, the CRESS response will be analyzed between efgartigimed and placebo using the full analysis set by means of a Cochran-Mantel-Haenszel test, stratified by IgG value at screening (> 16.0 g/L or  $\leq 16 \text{ g/L}$ ). The common odds ratio will be provided, along with the 95% CI.

In the event of missing values for the primary endpoint, only those participants who have a week 24 value will be included in the primary analysis. A sensitivity analysis, treating those participants with missing week 24 data as nonresponders, will be included.

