## 8.1. Disposition

The number of participants will be summarized for FAS and EAS. The number of participants per country and site will also be provided using the FAS. The number of participants who completed or discontinued the treatment and/or the study along with the reason for discontinuation will be summarized using the FAS.

Participant disposition and withdrawals will be presented for the FAS.

Data will be tabulated at least for:

- Number of participants in each analysis sets.
- number and percentage of participants randomized, completed, or discontinued the study.
- number and percentage of participants for each study discontinuation reason.
- number and percentage of participants discontinuing treatment but continuing study assessments.
- number and percentage of participants who roll over to OLE study ARGX-113-2211.

Participants not rolling over to the OLE study will have completed this study after the Safety Follow-up (SFV) or Early Discontinuation Visit (EDV).

A listing of participant disposition will be prepared to present information about treatment allocation, treatment discontinuation and study discontinuation.

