#### 14. EFFICACY OUTCOMES

#### 14.1. Primary Efficacy

The primary efficacy analyses will be performed for the EAS.

Document:

Author:

Version Number:

V2.0

Version Date:

31JAN2024

Template No.: CS TP BS016 Revision 7 Reference: CS WI BS005

Effective Date: 01Nov2021

Statistical Analysis Plan

Page 38 of 78

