Analysis Methodology:

The SAS procedure MI will be used and the details of MI procedure will be stated in the dataset specification document. The missing binomial outcomes will be imputed by multiple imputation method with the assumption of monotone missing pattern and logistic regression method. Multiple imputations would be conducted based on CRESS response (Yes/No). To reduce the sampling variability from the imputation process, 500 datasets will be generated.

Here in this case the numerator will include all the participants which are responders (imputed and actual responders) and the denominator will include all participants in FAS population.

In the estimation step, separate analysis will be performed using the statistical method mentioned for the primary endpoint statistical analysis.

Because the imputation of missing data is a key aspect to the analysis of the data, explicit details regarding this imputation are provided via sample SAS code that is intended to demonstrate the application of these strategies. Minor alterations to SAP code may be performed.

Example code for imputation of binary outcome which will be used for imputation by logistic regression is as follows:

Document:

Author:

Version Number:

V2.0

Template No.: CS TP BS016 Revision 7

Version Date: 31JAN2024

[figure not shown]
Reference: CS WI BS005

Effective Date: 01Nov2021

Statistical Analysis Plan

[figure not shown]
Page 45 of 78

Statistical Analysis Plan

Page 46 of 78

[figure not shown]

Effective Date: 01Nov2021

Statistical Analysis Plan

Page 47 of 78

The values obtained from back transformed dataset, will be used for reporting Unadjusted Odds Ratio and CIs.

If the planned hypothetical approach is not feasible due to data sparsity, then available data occurring on or after ICEs will be analyzed as observed (treatment policy). In this case, the numerator will include all the participants which are responders (actual responders only) and the denominator will be participants in EAS population.

Missing data unrelated to ICEs, will not be imputed.

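### The SAP moves the efficacy analyses from the protocol's full analysis set to an Efficacy Analysis Set whose eligibility criteria are not stated, and it mixes the two sets as denominators

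*SAP*

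**What the plan says.** **Protocol.** Section 9.2: "The full analysis set will be used to analyze endpoints related to the efficacy objectives". That set is everyone randomized and dosed. Section 9.3.2 names it again for the primary endpoint: the arms are compared "using the full analysis set by means of a Cochran-Mantel-Haenszel test", and the Wilson intervals are given for the same set.

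**SAP, definitions.** Section 5.2: "The full analysis set (FAS) will contain all randomized participants who received at least one dose of IMP and classified as Planned Treatment". Section 5.4: "The efficacy set contains all subjects from the FAS that are, based on pre-randomization information, eligible for efficacy evaluation". That one sentence is the whole definition of the EAS. Section 5 adds that agreement on who is "included/excluded from each analysis set for IA and Final Analysis, will be conducted prior to the unblinding of the study". Section 8.1 adds: "The number of participants will be summarized for FAS and EAS".

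**SAP, use.** Section 14.1: "The primary efficacy analyses will be performed for the EAS". Sections 14.2 and 14.3 put the secondary and exploratory efficacy analyses on the EAS too.

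**SAP, supplementary estimand (Primary Analysis text in 14.1.1).** The stated analysis set is the EAS. After multiple imputation, "the denominator will include all participants in FAS population". If imputation proves infeasible, the fallback uses the EAS as denominator.

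**The concern.** The protocol names one efficacy population, and the SAP analyses another that may be smaller. Nothing in the public text says which baseline tests, eligibility failures or deviations would make a randomized, dosed participant ineligible for efficacy, or who decides. Two statisticians could build different sets from SAP 5.4. With about 30 participants, one or two decisions show in the result.

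The timing leaves room for that discretion. SAP 5 sets the deadline at unblinding, not at collection of outcomes. SAP 4.2 places the interim analysis after every participant has completed week 24 or left the study, and lists database lock, analysis sets and unblinding in that order. Pooled, blinded week 24 results may therefore exist when membership is agreed.

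The conflict in the supplementary estimand is a separate fault and does not depend on what the EAS criteria turn out to be. If the two sets differ, the three instructions cannot all be followed. In addition, SAP 9 describes baseline characteristics on the FAS, so the baseline table may not describe the people analysed for efficacy.

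**Working it through.** **1. Which set is used where**

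| Analysis | Protocol | SAP |
|---|---|---|
| Primary CRESS comparison | FAS (9.2, 9.3.2) | EAS (14.1) |
| Secondary efficacy | FAS (9.2) | EAS (14.2) |
| Exploratory efficacy | FAS (9.2) | EAS (14.3) |
| Supplementary estimand, stated set | not defined | EAS |
| Supplementary estimand, denominator after imputation | not defined | FAS |
| Supplementary estimand, fallback denominator | not defined | EAS |
| Baseline characteristics | not specified | FAS (9) |

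For the main estimand the SAP says only that all participants enter the denominator whatever intercurrent events occur. It does not name the set there.

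**2. The plan's own precision figure**

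Inputs from protocol 9.5 and SAP 3.2: about 15 + 15 = 30 participants randomized 2:1, so 20 on efgartigimod and 10 on placebo; 50% response on efgartigimod; one-sided 95% Wilson limit, z = 1.645.

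Lower limit = [p + z²/(2n) − z√(p(1−p)/n + z²/(4n²))] / (1 + z²/n)

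With p = 0.5, n = 20, z² = 2.706: [0.5 + 0.0677 − 1.645 × √(0.0125 + 0.00169)] / 1.1353 = (0.5677 − 0.1960) / 1.1353 = 0.327. The plan's figure of about 33% is reproduced. It rests on all 20 randomized efgartigimod participants being analysed.

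**3. Excluding efgartigimod participants**

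The number excluded is an assumption; the documents give none. The same formula gives:

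| Excluded | All non-responders: rate (lower limit) | All responders: rate (lower limit) |
|---|---|---|
| 0 | 10/20 = 50.0% (32.7%) | 10/20 = 50.0% (32.7%) |
| 1 | 10/19 = 52.6% (34.7%) | 9/19 = 47.4% (30.1%) |
| 2 | 10/18 = 55.6% (36.9%) | 8/18 = 44.4% (27.2%) |
| 3 | 10/17 = 58.8% (39.3%) | 7/17 = 41.2% (24.1%) |

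The plan quotes placebo response rates of 24% to 32%. The limit for all 20 sits just above that range. One exclusion can move it inside the range or further clear of it.

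**4. Excluding a placebo participant**

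Assume 3/10 placebo responders. Dropping one non-responder gives 3/9 = 33.3%; dropping one responder gives 2/9 = 22.2%.

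Crude odds ratios, without the planned stratification:
- Full set, 10/20 v 3/10: (10 × 7)/(10 × 3) = 2.33, 95% CI 0.47 to 11.7.
- One efgartigimod responder dropped: (9 × 7)/(10 × 3) = 2.10.
- One efgartigimod non-responder dropped: (10 × 7)/(9 × 3) = 2.59.
- One placebo responder dropped: (10 × 7)/(10 × 2) = 3.50, 95% CI 0.58 to 21.2.

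**5. The mixed denominator**

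Suppose two efgartigimod participants are outside the EAS and 10 of the 18 inside it respond. The EAS proportion is 10/18 = 55.6%. If imputation is run on the EAS as stated and the result is divided by the FAS as stated, it is 10/20 = 50.0%. The 5.6-point gap comes only from the denominator, and it silently counts the two excluded people as non-responders.

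**The case against.** The strongest reply is that the EAS is constrained. SAP 5.4 admits only FAS members and only pre-randomization information, so compliance, dropout and week 24 response cannot be grounds for exclusion. SAP 5 requires agreement before unblinding. Such exclusions are not caused by treatment; they may change the target population and the precision. This stands. A reader might infer that the EAS has no membership rule, or that its use breaks the randomized comparison, and the documents support neither.

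A reader might also infer that membership will be settled after blinded outcomes have been seen. The text permits that but does not say it.

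Several other points are fair:
- Protocol 9 allows changes of method if the SAP describes them. The visible text of SAP 3.4 does not mention the change of set, but part of that list is missing from the public copy. Failure to disclose cannot be alleged.
- Protocol 9.3.2 itself limits the primary analysis to participants with a week 24 value, so the protocol did not promise an analysis of every dosed participant either.
- Protocol 5 forbids enrolment waivers, so the EAS may turn out identical to the FAS.
- The trial tests no formal hypothesis, and both set counts will be reported, so any exclusions will be visible.
- The FAS denominator after imputation may be a slip of wording.

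These points limit the likely harm. None supplies the missing criteria, restores a FAS version of the primary analysis, or tells the programmer which denominator to use.

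**Conclusion.** The plan is wrong as written on two counts: it departs from the protocol's efficacy analysis set, and its denominators conflict. What remains open is blinded discretion over which baseline facts make a dosed participant ineligible for efficacy.

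The possible size is modest per person but not negligible at this sample size. One efgartigimod exclusion shifts the observed rate by 2.6 points either way and the lower limit from 32.7% to 30.1% or 34.7%. One placebo exclusion shifts 30% to 22% or 33%. A reader might take one participant to be worth 5 points on efgartigimod or 10 on placebo, but those are the effects of reclassifying a response, not of dropping a person. The figures assume 10/20 and 3/10 responders and an arbitrary number of exclusions. They show what could happen, not an expected bias. If the EAS equals the FAS, the numerical effect is nil and only the wording needs repair.

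**What to change.** - In SAP 14.1, 14.2 and 14.3, run the efficacy analyses on the FAS as SAP 5.2 and 5.5 define it, by planned treatment. Reconcile this with protocol 9.2, which assigns participants by the IMP they actually received, and record the resolution in SAP 3.4 if it is not already there.
- Use that one set as the denominator for the main estimand, the supplementary estimand after imputation, and the fallback. Name it in each place.
- Keep the EAS as a sensitivity analysis only, and list its objective pre-randomization criteria in SAP 5.4.

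The cost is SAP wording and relabelled outputs, plus one sensitivity table. No new data are needed.

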## 5.5.PK Analysis Set [PKAS]- efgartigimod

The PK analysis set (PKAS) used for the descriptive summaries of efgartigimod serum concentrations will consist of all randomized participants who receive at least one dose of efgartigimod and have at least 1 measured concentration of efgartigimod at a scheduled PK time point after start of dosing without protocol violations or events with potential to affect the PK concentration. Participants in this population will be used for all PK summaries.

When using the FAS, participants will be classified according to their planned treatment arm. For analyses performed on the SAF or PKAS, the actual treatment arm will be considered. The actual treatment arm will be the same as the planned treatment arm unless the participant received IMP other than the planned one for the whole study.

#### 6. GENERAL CONSIDERATIONS

### 6.1. Reference Start Date and Study Day

Study Day will be calculated from the reference start date and will be used to show start/stop day of assessments and events. It will appear in every listing where an assessment date or event date appears.

Reference start date is defined as the day of the first dose of IMP.

- If the date of the event is on or after the reference date, then:
  - $\circ$  Study Day = (date of event reference date) + 1

Document:

Author:

Version Number:

V2.0

Version Date:

31JAN2024

Template No.: CS TP BS016 Revision 7 Reference: CS WI BS005

Effective Date: 01Nov2021

Statistical Analysis Plan

Page 25 of 78

- If the date of the event is prior to the reference date, then:
  - Study Day = (date of event reference date)

In the situation where the event date is partial or missing, the date will appear partial or missing in the listings, and Study Day

Date implies a complete date having day, month and year available. Unless otherwise specified, the study day will remain missing when it cannot be calculated due to absence or incompleteness of the concerned and/or

reference dates.

In case the participant never received IMP, the date/time of randomization will be used instead of first IMP administration date/time.

End of study (EOS) is defined as date of participant's last visit. This is date of treatment period completion and/or safety follow-up or early discontinuation visit. A participant will have completed the study if the treatment period (or follow-up period, if applicable) has been completed.

- Participants rolling over to the OLE study will have completed treatment period in this study at week 24.
- Participants not rolling over to the OLE study will have completed this study after the Safety Follow-up visit
  (SFV) or Early Discontinuation visit (EDV). If a participant continued in the study after discontinuing IMP, this
  will be week 24 or at the SFV (if permanent IMP discontinuation is < 56 days from week 24).

End of treatment (EOT) is defined as date of treatment completion or date of permanent discontinuation of IMP.

